10.2.3 Adverse Events of Special Interest

Adverse events of special interest (AESIs) will be composite events made up of TEAEs meeting the following MedDRA search strategies.

- GI events will include the MedDRA preferred terms (PTs) in the GI and GI procedure related events Company MedDRA Query (CMQ 80000145). This summary will be done for the LCIG group only.
- POLY events will include the PTs in either the Peripheral Neuropathy Standard MedDRA Query (SMQ 20000034) broad search or Guillain-Barre Syndrome SMQ (SMQ 20000131) broad search.
- WEIGHT events will include the PTs in the Weight loss CMQ (CMQ 80000109).

For each AESI, the number and percentage of subjects experiencing one or more adverse events during the 12-week Treatment Period will be summarized for each treatment group and for overall subjects by primary SOC and PT for overall treatment period interval. Similar summaries will be prepared for all TEAEs that are not GI events as well as for all TEAEs that are in either the Peripheral Neuropathy Standard MedDRA Query (SMQ 20000034) narrow search or Guillain-Barre Syndrome SMQ (SMQ 20000131) narrow search.

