4.0 Study Objectives, Design and Procedures

4.1 Objectives

The primary objective of this interventional study is to examine the effect of LCIG treatment relative to that of Optimized Medical Treatment (OMT) on dyskinesia as measured by the Unified Dyskinesia Rating Scale (UDysRS) Total Score.

The Secondary objective is to assess the effect of LCIG treatment relative to that of OMT on dyskinesia as measured by PD Diaries, motor symptoms, motor complications, health-related outcome measures, safety and tolerability.

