10.2.1 Adverse Event Overview

The number and percentage of subjects experiencing one or more adverse events in the following adverse event categories during the 12-week Treatment Period will be summarized.

- Any TEAE
- Any TEAE that was rated by the investigator as having a reasonable possibility of relationship to levodopa-carbidopa intestinal gel
- Any severe TEAE
- Any serious TEAE
- Any TEAE that led to discontinuation of study drug
- Any treatment emergent GI event (as defined in Section 10.2.3)
- Any TEAE other than a GI event (as defined in Section 10.2.3)
- A fatal TEAE
- All deaths

The number and percentage of subjects experiencing one or more adverse events in the following adverse event categories during the Transition Period will be summarized.

- Any TEAE
- Any TEAE that was rated by the investigator as having a reasonable possibility of relationship to levodopa-carbidopa intestinal gel
- Any severe TEAE
- Any serious TEAE
- Any TEAE that led to discontinuation of study drug
- Any treatment emergent GI event (as defined in Section 10.2.3)
- Any TEAE other than a GI event (as defined in Section 10.2.3)

- A fatal TEAE
- All deaths

Serious adverse events with onset during the Screening Period for all subjects screened, adverse events and serious adverse events with onset after day of randomization and before day of initial device placement for the LCIG group, as well as adverse events during the transition period for LCIG subjects continuing LCIG commercial treatment will also be summarized.

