10.2.2 Adverse Event Incidence

The number and percentage of subjects experiencing one or more adverse events in the following adverse event categories during the 12-week Treatment Period will be summarized for each treatment group and for overall subjects by primary SOC and PT for overall treatment interval.

- Any TEAE
- Any serious TEAE
- Any TEAE that led to discontinuation of study drug

The percentage of subjects in the LCIG group and in the OMT group will be compared using Fisher's exact test. Only *P* values ≤ 0.100 when rounded to three digits will be presented.

The number and percentage of subjects experiencing one or more adverse events in the following adverse event categories during the Transition Period will be summarized for LCIG subjects who enter the Transition Period by primary SOC and PT.

[figure not shown]
- Any TEAE
- Any serious TEAE
- Any TEAE that led to discontinuation of study drug

The number and percentage of subjects experiencing one or more TEAEs during the 12-week Treatment Period will also be summarized for each treatment group and for overall subjects by maximum severity category (mild, moderate, severe, or unknown) and primary SOC and PT for overall treatment interval. Subjects reporting more than one TEAE for a given PT will be counted only once for that term in the most severe category reported. If a subject has an adverse event with unknown severity, then the subject will be counted in the severity category of "unknown," even if the subject has another occurrence of the same event with a severity present. The only exception is if the subject has another occurrence of the same adverse event with the most extreme severity -"Severe." In this case, the subject will be counted under the "Severe" category.

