10.2.5 Listings of Adverse Events

The following additional summaries of adverse events will be prepared.

- Listing of all deaths for all subjects screened
- Listing of all serious TEAEs
- Listing of all TEAEs that led to discontinuation of study drug
- Listing of all GI AESIs (as defined in Section 10.2.3)
- Listing of all POLY AESIs (as defined in Section 10.2.3)
- Listing of all WEIGHT AESIs (as defined in Section 10.2.3)

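### The composite GI AESI summary is limited to the LCIG arm, so the plan does not secure the OMT rate for the only AESI classed as a known risk

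*SAP*

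**What the plan says.** SAP 10.2.3 builds three AESIs from MedDRA queries: GI (a company query for GI and GI-procedure-related events), polyneuropathy and weight loss. Only the GI bullet carries a restriction: "This summary will be done for the LCIG group only". The following paragraph states the general rule that, for each AESI, the number and percentage of subjects "will be summarized for each treatment group and for overall subjects by primary SOC and PT for overall treatment period interval". It then treats the complement the same way: "Similar summaries will be prepared for all TEAEs that are not GI events".

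Elsewhere in the plan:

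- SAP 4.1: the secondary objective is "to assess the effect of LCIG treatment relative to that of OMT" on a list of outcomes that includes safety and tolerability.
- SAP 10.2.1: the overview has a row for any treatment-emergent GI event, defined by reference to 10.2.3. The overview's columns are not stated.
- SAP 10.2.2: all treatment-emergent events are tabulated by system organ class (SOC) and preferred term for each arm. "The percentage of subjects in the LCIG group and in the OMT group will be compared using Fisher's exact test". P values above 0.100 are not shown, but the counts are.
- SAP 10.2.5: a listing of all GI AESIs, with no arm restriction.
- Protocol 8.1.4 and 8.1.4.2: a between-arm Fisher's exact test is the default for binary safety variables. The AESI summary has no arm limit, and the SAP is left to define the search criteria.
- SAP 12.0: no change in analysis from the protocol.

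**The concern.** GI is the only AESI that Protocol 3.2 places under known risks; polyneuropathy and weight loss are listed as potential risks. The same section attributes the common events seen on LCIG either to underlying Parkinson's disease or to PEG-J placement. Separating those two sources is what a randomised control is for, and the adverse events are collected in both arms. A one-arm percentage for the GI composite cannot be set against a background rate.

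The layout is also uneven. The other two AESIs and the non-GI complement would have both arms, and the GI composite would have one. No reason is given, and the restriction is not recorded as a departure from the protocol.

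**Working it through.** No document figure depends on this restriction, so the check is mainly a comparison of texts. Arithmetic is used only to show what the remaining outputs can and cannot supply.

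**1. Are the texts compatible?** The bullet in SAP 10.2.3 limits the GI summary to LCIG, while the next paragraph applies to each AESI and names both arms without an exception. Protocol 8.1.4.2 sets no arm limit and delegates search criteria, not the choice of arms. If the bullet governs, the SAP departs from the protocol and 12.0 should say so. If the paragraph governs, the bullet is an error. The text does not settle which.

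**2. What GI information remains for OMT?**

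| Output | By arm? | Gives subjects with any GI AESI? |
|---|---|---|
| 10.2.2 preferred-term rows | Yes, with Fisher tests | No: one subject can be in several rows |
| 10.2.2 SOC totals | Yes | No: counted once within an SOC, but the query is not defined as an SOC |
| 10.2.1 GI row | Not stated | Yes, if shown by arm |
| 10.2.5 listing | No restriction stated | Only by hand count |
| 10.2.3 GI table | LCIG only, per the bullet | LCIG only |

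**3. Can rows be summed?** SAP 10.2 counts a subject once per preferred term. For two terms with rates a and b in the same group, the share with either lies between max(a, b) and min(a + b, 100%). Protocol 3.0 gives nausea 29.7% and constipation 21.6% for the pivotal study:

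- lower limit: max(29.7, 21.6) = 29.7%
- upper limit: 29.7 + 21.6 = 51.3%

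Two terms already leave a range of 51.3 − 29.7 = 21.6 points. Adding abdominal pain (51.4%) gives a range from 51.4% to 100%, since 51.3 + 51.4 = 102.7 exceeds 100.

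**4. What could a two-arm comparison show at this size?** SAP 4.3 assumes a difference of 10, SD 12 and 27 per group. The t-test noncentrality is (10/12) × √(27/2) = 3.06 on 52 degrees of freedom, which gives power 85.2% and reproduces the stated 85%. Then 27/0.90 = 30 per arm. LCIG subjects without a tube placement leave the safety dataset, so 30 is an upper figure for that arm.

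No composite rate is given in the documents. As a stand-in, take 29.7% for LCIG and assume 0% to 20% for OMT. The half-width is 1.96 × √[p₁(1 − p₁)/30 + p₂(1 − p₂)/30].

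| Assumed OMT rate | Difference (points) | 95% half-width | Fisher power |
|---|---|---|---|
| 0% | 29.7 | 16.4 | 92% |
| 5% | 24.7 | 18.1 | 62% |
| 10% | 19.7 | 19.6 | 36% |
| 20% | 9.7 | 21.7 | 9% |

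An LCIG-only column reads 29.7% in every row. The interval at 0% is only approximate; for 0 of 30, the exact two-sided 95% upper limit is 1 − 0.025^(1/30) = 11.6%.

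**The case against.** The strongest reply has four parts.

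- **The control is still used where it matters most.** SAP 10.2.2 gives both arms' rates and a Fisher test for every preferred term. Comparing the all-event table with the non-GI table even shows which terms belong to the GI query. This stands. A reader might infer that the randomised control is thrown away for GI safety, but the documents do not support that. The loss is the composite only.
- **The bullet may be a deliberate exception.** A specific restriction followed by a general rule can be read that way. This stands in part: it is a conflict as written, not proof of an error. Even so, an exception needs a reason and an entry in SAP 12.0.
- **OMT subjects have no tube, so the procedural part is zero by design.** True, and an undivided composite would mix procedure events with other GI events. But Protocol 6.4 treats drug, device and placement as one system, so the zero belongs to the comparison. The remedy is a split, not removal of the column.
- **The query's terms are not in the documents.** True. That it covers nausea, constipation and similar terms is inferred from its title, which names GI events as well as GI procedure events.

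Two further inferences should be avoided. The open-label rates in Protocol Table 2 come from a mean exposure of 854 days and do not predict 12-week rates. And GI events are not ranked as the main risk: Protocol 3.2 lists seven important identified risks in no stated order of importance.

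**Conclusion.** The point holds in a limited form. SAP 10.2.3 restricts the composite GI AESI summary to LCIG, in conflict with its own next paragraph and with the protocol's unrestricted AESI summary, and SAP 12.0 does not acknowledge it. The consequence is that the de-duplicated GI AESI rate in OMT is not secured as a planned summary. Preferred-term rows cannot replace it, and the overview row does so only if its unstated columns are by arm.

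The size cannot be put as one number, because the documents give no composite rate and no OMT rate. Under the stand-in of 29.7% on LCIG and an assumed 0% to 20% on OMT, the difference that a one-arm table leaves open runs from 29.7 down to 9.7 points. This rests on about 30 subjects per arm and on treating the pivotal-study nausea figure as an LCIG rate; the protocol does not name the arm. For nausea itself SAP 10.2.2 will show both arms, so the figures illustrate the problem and do not measure a loss on that term. Nothing in the efficacy analysis, power or type I error changes.

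**What to change.** 1. In SAP 10.2.3, delete "This summary will be done for the LCIG group only" and produce the GI AESI summary for LCIG, OMT and overall, as for the other two AESIs.
2. Split that summary into procedure/device-related terms (zero by design in OMT) and other GI terms. List the terms in each part before database lock.
3. In SAP 10.2.1, state that the overview, including its GI row, is shown by treatment group.
4. If the restriction is intended, state the exception and its reason in 10.2.3 and record it in 12.0.

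The cost is one more column from data already collected, plus the work of dividing the query terms. Two cautions go with it. The undivided composite must not be read as a pure drug effect. Terms that can arise either from the procedure or from other causes, such as abdominal pain, will need a stated home in the split.

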10.2.4 Adverse Events by Subgroup

The number and percentage of subjects in each of the following subgroups experiencing one or more TEAEs during the 12-week Treatment Period will be summarized for each treatment group and for overall subjects by primary SOC and PT.

- Gender (male, female)
- Age category (< 65 years, \geq 65 years)
- Baseline BMI category (< 25 kg/m², \geq 25 kg/m²)
- Duration of Parkinson's disease (< 10 years, \geq 10 years)

10.2.5 Listings of Adverse Events

The following additional summaries of adverse events will be prepared.

- Listing of all deaths for all subjects screened
- Listing of all serious TEAEs
- Listing of all TEAEs that led to discontinuation of study drug
- Listing of all GI AESIs (as defined in Section 10.2.3)
- Listing of all POLY AESIs (as defined in Section 10.2.3)
- Listing of all WEIGHT AESIs (as defined in Section 10.2.3)

10.3 Analysis of Laboratory Tests

Hematology variables include: partial thromboplastin time (PTT), hematocrit, hemoglobin, international normalized ratio (INR), mean corpuscular hemoglobin (MCHC), mean corpuscular volume (MCV), platelet count, prothrombin time (PT), red blood cell (RBC) count, white blood cell (WBC) count and WBC differentials.

Chemistry variables include: albumin, alkaline phosphatase, bicarbonate, total bilirubin, blood urea nitrogen (BUN), calcium, chloride, cholesterol, creatine phosphokinase (CPK), creatinine, gamma-glutamyl transpeptidase (GGT), glucose, lactate dehydrogenase (LDH), inorganic phosphorus, potassium, serum glutamic-oxaloacetic transaminase (SGOT/AST), serum glutamic pyruvic transaminase (SGPT/ALT), total protein, sodium, TSH, free T4, triglycerides and uric acid.

Urinalysis variables include: blood, glucose, ketones, pH, protein, specific gravity, and the results of microscopic analysis.

Special laboratory variables include: Vitamin B₁₂, Vitamin B₆, methylmalonic acid (MMA), folic acid and homocysteine levels.

10.3.1 Analysis of Mean Changes for Laboratory Tests

Analyses of mean change from baseline to each planned visit and to the minimum, maximum and final value during the 12-week Treatment Period will be presented by treatment group for each continuous hematology, chemistry, urinalysis, and special laboratory variable.

For each change from baseline analysis, the following summary statistics for each treatment group will be presented: sample size, baseline mean, visit mean, and the mean, standard deviation, and median of the change from baseline. The baseline and visit means will be calculated for each visit for subjects who have both a baseline and visit value. The mean changes for the LCIG group and for the OMT group will be compared using an ANOVA with treatment as the factor. LS mean, standard error, 95% confidence interval and *P* value will be presented.

[figure not shown]
Analyses of mean change from baseline to each planned visit and to the minimum, maximum and final value during the Transition Period will be presented for each continuous special laboratory variable for LCIG subjects who enter the Transition Period.

10.3.2 Shifts Between Normal and Abnormal for Laboratory Tests

Laboratory observations will be categorized as normal, low, or high relative to the reference (normal) range associated with the laboratory that performed the assay. For each hematology, chemistry, urinalysis and special laboratory variable with a reference range, shift tables will be prepared for shifts from baseline to lowest, highest and final value during the 12-week Treatment Period for each treatment group and overall subjects.

The tables will present:

- The numbers and percentages of subjects with low or normal observations at baseline who have a high observation at any post-baseline visit
- The numbers and percentages of subjects with normal or high observations at baseline who have a low observations at any post-baseline visit

- The numbers and percentages of subjects with low or normal observations at baseline who have a high observation at the final visit
- The numbers and percentages of subjects with normal or high observations at baseline who have a low observations at the final visit

10.3.3 Potentially Clinically Significant (PCS) Laboratory Values

Criteria for potentially clinically significant (PCS) values have been predefined for selected laboratory variables as outlined in Appendix C. For each variable, a summary of the number and percentage of subjects in each treatment group who have at least one post-baseline observation during the 12-week Treatment Period that meets the PCS criteria and is more extreme than their baseline value will be provided.

A summary of the number and percentage of subjects who have at least one observation during the Transition Period that meets the PCS criteria and is more extreme than their baseline value will be provided for LCIG subjects who enter the Transition Period.

A listing will also be prepared that will include, for each variable, all observations for each subject that met the PCS criteria for that variable at any time during the study. No comparisons of treatment groups will be performed.

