So far no prospective controlled data have been generated on the efficacy of LCIG on dyskinesia. Preliminary evidence from post-hoc analyses from both interventional²⁵ and observational studies suggests that LCIG may decrease duration and severity of dyskinesia for up to 2 years. ^{25,26} This will be the first large interventional controlled study of LCIG for advanced Parkinson's disease patients specifically investigating the effectiveness on dyskinesia.

3.2 **Benefits and Risks**

Benefits

LCIG provides continuous rather than intermittent stimulation of the dopaminergic receptors in the brain by maintaining constant plasma concentrations of levodopa. The infusion of the gel formulation, allows a greater flexibility in individualized dosing, thereby allowing the plasma concentration to be within the narrow therapeutic window of these advanced PD patients.

Efficacy of LCIG treatment on motor symptoms in subjects with advanced PD has been demonstrated in Phase 3 studies. In the pivotal Phase 3 study (Studies S187-3-001/S187-3-002), compared to LC-IR, LCIG treatment significantly improved "Off" time (LS Mean difference = -1.91 hours) and "On" time without troublesome dyskinesia (LS Mean difference = 1.86 hours) at Week 12. LCIG treatment also demonstrated a statistically and clinically significant impact on subject's quality of life as assessed with the PDQ-39 summary index and the UPDRS Part II score. Subjects with advanced Parkinson's disease who qualify for the study are expected to benefit

through better control of the motor fluctuations that are not adequately controlled with other PD medications.

Risks

Due to the long experience with the oral drug combination of levodopa and carbidopa for the treatment of PD, the risks that are associated with both active pharmaceutical ingredients are well known. These and additional information on risks are available in the Investigator's Brochure.²⁷

Important Identified Risks

- Gastrointestinal, Gastrointestinal Device, and Gastrointestinal Procedure Related Events
- Dyskinesia
- Psychosis Associated Events
- Impulsive Control Disorders (ICDs)
- Orthostatic Hypotension
- Sudden Onset of Sleep/Somnolence
- Neuroleptic Malignant Syndrome (NMS)

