samples should be collected after the completion of all other assessments. The Investigator must review the laboratory assessments (initialed and dated) after the receipt of results.

All laboratory abnormalities that occur during the study must be evaluated by the Investigator to determine if they indicate a new disease process, an exacerbation or worsening of an existing condition, or require further action to be taken and therefore may need to be reported as adverse events. Accordingly, for any values outside of the reference range, the Investigator will indicate on the report if the result is Clinically Significant (CS) or Not Clinically Significant (NCS). If a laboratory abnormality meets criteria for a Potentially Clinically Significant (PCS) laboratory value, as defined in Appendix D, the Investigator must either report an associated adverse event or document in source the reason(s) the finding was not considered an adverse event.

The PT/PTT will be performed only Screening Visit 1.

Any laboratory value that remains abnormal at Premature Discontinuation/End of Study and was judged to be clinically significant will be followed according to accepted medical standards until resolution of the abnormality.

Table 5. Clinical Laboratory Tests

Hematology	Clinical Chemistry	Urinalysis	Special Tests ^d
Hematocrit Hemoglobin Red Blood Cell (RBC) count Platelet count (estimate not acceptable) White Blood Cell (WBC) count Mean corpuscular volume (MCV) Mean corpuscular hemoglobin (MCHC) Neutrophils Bands Lymphocytes Monocytes Basophils Eosinophils PT/INR (Prothrombine Time/International Normalized Ratio) ^a PTT (Partial Thromboplastin Time) ^a	Blood Urea Nitrogen (BUN) Creatinine Total bilirubin Serum glutamic-pyruvic transaminase (ALT) Serum glutamic-oxaloacetic transaminase (AST) Alkaline phosphatase Sodium Potassium Calcium Inorganic phosphorus Uric acid Cholesterol Total protein Glucose Triglycerides Albumin Chloride Creatine kinase Gamma-glutamyl transpeptidase (GGT) Bicarbonate Lactate dehydrogenase LDH Pregnancy test Beta human chorionic gonadotropin (hCG)	Specific gravity Ketones pH Protein Blood Glucose Microscopic Examination Urine pregnancy Test ^c Drug/Alcohol screening ^d Ethanol U-etylglucuronide (U Etg) U-etylsulphate (U-Ets) Cannabinoids Barbiturates Benzodiazepines Opiates Methadone Cocaine Amphetamines	Thyroid Function Tests ^e Vitamin B ₁₂ f Vitamin B ₆ f Folic Acid Methylmalonic Acid (MMA) f Homocysteine f

- a. Only done at Visit 1.

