GGT increased	2	$> 2.5 \times ULN$	$>$ ULN $-2.5 \times$ ULN	$> 2.5 - 5.0 \times ULN$	$> 5.0 - 20.0 \times ULN$	$> 20.0 \times ULN$
				Corrected Serum Calcium of:	um of:	
Hypercalcemia	3	> 12.5 mg/dL	> ULN – 11.5 mg/dL	> 11.5 - 12.5 mg/dL	> 12.5 – 13.5 mg/dL	> 13.5 mg/dL
		> 3.1 mmol/L	> ULN – 2.9 mmol/L	> 2.9 – 3.1 mmol/L	> 3.1 – 3.4 mmol/L	> 3.4 mmol/L
				Ionized Calcium		
		> 1.6 mmol/L	> ULN - 1.5 mmol/L	> 1.5 - 1.6 mmol/L; symptomatic	> 1.6 - 1.8 mmol/L; hospitalization indicated	> 1.8 mmol/L; life-threatening
						consequences

CTCAE v4.0 Term	PCS Value/Grade	PCS Value	Grade 1	Grade 2	Grade 3	Grade 4
Chemistry (continued)						
			Fasting Glucose Value	cose Value		
Hyperglycemia	3	> 250 mg/dL	> ULN - 160 mg/dL	> 160 - 250 mg/dL	> 250 - 500 mg/dL	> 500 mg/dL
		> 13.9 mmol/L	> ULN - 8.9 mmol/L	> 8.9 – 13.9 mmol/L	> 13.9 – 27.8 mmol/L; hospitalization indicated	> 27.8 mmol/L; life-threatening consequences
Hyperkalemia	3	> 6.0 mmol/L	> ULN - 5.5 mmol/L	> 5.5 – 6.0 mmol/L	> 6.0 - 7.0 mmol/L; hospitalization indicated	> 7.0 mmol/L; life-threatening consequences
Hypermagnesemia	3	> 3.0 mg/dL	> ULN - 3.0 mg/dL	1	> 3.0 - 8.0 mg/dL	> 8.0 mg/dL
		> 1.23 mmol/L	> ULN - 1.23 mmol/L		> 1.23 – 3.30 mmol/L	> 3.30 mmol/L; life-threatening consequences
Hypernatremia	С	> 155 mmol/L	> ULN - 150 mmol/L	> 150 – 155 mmol/L	> 155 – 160 mmol/L; hospitalization indicated	> 160 mmol/L; life-threatening consequences
Hypertriglyceridemia	3	> 500 mg/dL mg/dL	150 – 300 mg/dL	> 300 – 500 mg/dL	> 500 – 1000 mg/dL	> 1000 mg/dL
		> 5.7 mmol/L	1.71 – 3.42 mmol/L	> 3.42 – 5.7 mmol/L	> 5.7 – 11.4 mmol/L	> 11.4 mmol/L; life-threatening consequences
Hyperuricemia (Uric	4	> 10 mg/dL	> ULN - 10 mg/dL	1	> ULN -10 mg/dL (0.59	> 10 mg/dL
Acid Increased)		> 0.59 mmol/L	(0.59 mmol/L) without physiologic consequences		mmol/L) with physiologic consequences	> 0.59 mmol/L; life-threatening consequences

CTCAE v4.0 Term	PCS Value/Grade	PCS Value	Grade 1	Grade 2	Grade 3	Grade 4
Chemistry (continued)						
Hypoalbuminemia	3	< 2 g/dL	< LLN – 3 g/dL	<3-2 g/dL	<2 g/dL	Life-threatening
		$< 20 \mathrm{~g/L}$	< LLN – 30 g/L	<30 – 20 g/L	< 20 g/L	consequences; urgent intervention indicated
				Corrected Serum Calcium	cium	
Hypocalcemia	3	< 7.0 mg/dL	< LLN – 8.0 mg/dL	< 8.0 – 7.0 mg/dL	< 7.0 - 6.0 mg/dL	< 6.0 mg/dL
		< 1.75 mmol/L	< LLN – 2.0 mmol/L	< 2.0 – 1.75 mmol/L	< 1.75 – 1.5 mmol/L	< 1.5 mmol/L
				Ionized Calcium		

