		< 0.9 mmol/L	< LLN – 1.0 mmol/L	< 1.0 – 0.9 mmol/L;	< 0.9 – 0.8 mmol/L;	< 0.8 mmol/L;
				symptomatic	hospitalization indicated	life-threatening consequences
Hypoglycemia	3	< 40 mg/dL	< LLN – 55 mg/dL	< 55 – 40 mg/dL	< 40 - 30 mg/dL	< 30 mg/dL
		< 2.2 mmol/L	< LLN – 3.0 mmol/L	< 3.0 – 2.2 mmol/L	< 2.2 - 1.7 mmol/L	< 1.7 mmol/L; life-threatening consequences; seizures
Hypokalemia	8	< 3.0 mmol/L	< LLN – 3.0 mmol/L	< LLN – 3.0 mmol/L; symptomatic; intervention indicated	< 3.0 – 2.5 mmol/L; hospitalization indicated	< 2.5 mmol/L; life-threatening consequences
Hypomagnesemia	3	< 0.9 mg/dL	< LLN - 1.2 mg/dL	< 1.2 – 0.9 mg/dL	$< 0.9 - 0.7 \mathrm{mg/dL}$	< 0.7 mg/dL
		< 0.4 mmol/L	< LLN – 0.5 mmol/L	< 0.5 – 0.4 mmol/L	< 0.4 – 0.3 mmol/L	< 0.3 mmol/L; life-threatening consequences
Hyponatremia	3	< 130 mmol/L	< LLN – 130 mmol/L	ŀ	< 130 – 120 mmol/L	< 120 mmol/L; life-threatening consequences

CTCAE v4.0 Term	PCS Value/Grade	PCS Value	Grade 1	Grade 2	Grade 3	Grade 4
Chemistry (continued)						
Hypophosphatemia	3	< 2.0 mg/dL	< LLN – 2.5 mg/dL	< 2.5 - 2.0 mg/dL	< 2.0 - 1.0 mg/dL	< 1.0 mg/dL
		< 0.6 mmol/L	< LLN – 0.8 mmol/L	< 0.8 – 0.6 mmol/L	< 0.6 – 0.3 mmol/L	< 0.3 mmol/L; life-threatening consequences
Enzymes						
Alanine	2	> 3 × ULN	> ULN - 3.0 × ULN	$> 3.0 - 5.0 \times ULN$	> 5.0 – 20.0 × ULN	> 20.0 × ULN
aminotransferase (ALT) increased						
Alkaline phosphatase increased	2	> 2.5 × ULN	> ULN – 2.5 × ULN	$> 2.5 - 5.0 \times \text{ULN}$	$> 5.0 - 20.0 \times \text{ULN}$	> 20.0 × ULN
Aspartate aminotransferase (AST) increased	2	> 3 × ULN	> ULN – 3.0 × ULN	> 3.0 – 5.0 × ULN	> 5.0 – 20.0 × ULN	> 20.0 × ULN
CPK increased	3	> 5 × ULN	> ULN – 2.5 × ULN	$> 25 \times \text{ULN} - 5 \times \text{ULN}$	$> 5 \times \text{ULN} - 10 \times \text{ULN}$	> 10 × ULN

Adapted from the Common Terminology Criteria for Adverse Events (CTCAE) Version 4.0 Published: May 28, 2009 (v4.03: June 14, 2010)

Common Terminology Criteria for Adverse Events (CTCAE) Version 4.0 Published: May 28, 2009 (v4.03: June 14, 2010).

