6.5 Analysis by Planned Visit for Non-Diary Variables

A midpoint convention will be used to assign all observations to a planned visit based on the Study Day of the observation. If there are multiple observations on the same day, the average will be taken and considered the observation for the day. If more than one observation is assigned to a planned visit, the last observation will be selected and considered the observation for the planned visit.

The following Study Day windows will be used to assign efficacy and health outcome assessments to planned study visits during the 12-week Treatment Period. Assessments

on the day of first day of LCIG infusion via PEG-J are not planned and will not be included in the analysis.

Assessment	Planned Visit	Nominal Study Day	Study Day Range ^a
UDysRS, UPDRS,	Baseline		\leq date of randomization
mAIMS, CGI-C	Week 2	14	2 - 21
	Week 4	28	22 - 42
	Week 8	56	43 - 70
	Week 12	84	≥ 71
PDQ-8	Baseline		\leq date of randomization
	Week 8	56	2 - 70
	Week 12	84	≥ 71
King's PD Pain Scale	Baseline		\leq date of randomization
	Week 4	28	2 - 42
	Week 8	56	43 - 70
	Week 12	84	≥ 71

a. For subjects in LCIG group, all post-baseline assessments must also be after start of LCIG infusion through PEG-J and no more than 1 day after the date of the last LCIG infusion in the 12-week Treatment Period.

The following Study Day windows will be used to assign safety assessments during the
12-week Treatment Period to planned study visits.

Assessment	Planned Visit	Nominal Study Day	Study Day Range ^a
Vital signs and weight,	Baseline		\leq date of randomization
MIDI, Sleep Attacks	Week 2	14	2 - 21
Questionnaire, C-SSRS	Week 4	28	22 - 42
	Week 8	56	43 - 70
	Week 12	84	≥ 71
	Week 13 FU ^b	91	$2 \leq RxEnd Days$
Clinical labs and	Baseline		\leq date of randomization
Electrocardiograms, Special labs	Week 8	56	1 - 70
Special laus	Week 12	84	≥ 71

For subjects in LCIG group, all post-baseline assessments must also be no more than 1 day after the final PEG-J a. removal for subjects who do not transit to commercial product or no more than 1 day after the final Study M15-535 LCIG infusion during 12-week Treatment Period for subjects who transit to commercial product.

b. Applicable only to LCIG subjects who will not continue on commercial product.

For LCIG subjects who enter the Transition Period, vital signs and weight, special labs, C-SSRS and MIDI will be assessed every 12 weeks.

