Appendix B. **Potentially Clinically Significant Laboratory Values**

NA = not applicable; ULN = upper limit of normal

Adapted from the Common Terminology Criteria for Adverse Events (CTCAE) Version 4.0 Published: May 28, 2009 (v4.03: June 14, 2010).

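### SAP Appendix B drops the protocol's PCS limits for CPK and GGT without explanation, and the planned Transition Period PCS laboratory summary has no scheduled data to fill it

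*SAP*

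**What the plan says.** **Limits in the protocol.** Protocol Appendix D sets PCS laboratory limits for this study. They include rows headed "CPK increased" (> 5 x ULN) and "GGT increased" (> 2.5 x ULN). Protocol 5.3.1.1 (Clinical Laboratory Tests) attaches a site duty to these limits: when one is met, the investigator reports an associated adverse event or records in source why not.

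**Limits in the SAP.** SAP 10.3.3 says: "Criteria for potentially clinically significant (PCS) values have been predefined for selected laboratory variables as outlined in Appendix C". Appendix C is the vital sign and weight table. The laboratory table, titled "Potentially Clinically Significant Laboratory Values", is Appendix B, and it has no row for CPK or GGT. Section 10.3.3 counts subjects with a post-baseline value that meets a criterion and is more extreme than baseline. It also lists every value meeting a criterion at any time in the study.

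**Transition Period.** SAP 10.3.3 adds: "A summary of the number and percentage of subjects who have at least one observation during the Transition Period that meets the PCS criteria". The same baseline condition applies there. On what is collected in that period, SAP 6.5 says that "vital signs and weight, special labs, C-SSRS and MIDI will be assessed every 12 weeks". Protocol Table 4 agrees: its transition column marks the special laboratory tests and not the clinical labs.

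**Latitude and changes.** Protocol 8.1.4.3 leaves the SAP to pre-specify PCS criteria for selected laboratory variables. SAP 12.0 declares no change in analysis from Protocol Amendment 1.

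**The concern.** The protocol and the SAP give different lists of PCS limits, and the SAP does not explain the difference. Someone who reads SAP 12.0 will reasonably expect the Appendix D limits to drive the PCS tables. For CPK and GGT they do not. A value above the protocol's limit that the investigator chose not to call an adverse event would be missing from both the PCS table and the PCS listing.

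The Transition Period has a different problem. A summary is promised, but the plan supplies no matching combination of test and criterion. A table with no entries can be read as an absence of abnormalities when nothing was evaluable. Meanwhile the one laboratory panel that is drawn in that period has no categorical laboratory display. Protocol 5.3.1.1 ties that panel to vitamin deficiency and to the work-up of polyneuropathy symptoms, and polyneuropathy is an adverse event of special interest (protocol 6.2.3).

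**Working it through.** The plan states no figure on this point, so the check is a comparison of lists. Low and high limits count separately; total and ionized calcium count once.

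**1. Protocol Appendix D against SAP Appendix B**

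| | Hematology | Chemistry | Enzymes | Total |
|---|---|---|---|---|
| Protocol Appendix D | 10 | 18 | 4 | 32 |
| SAP Appendix B | 10 | 15 | 3 | 28 |

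Missing from the SAP: 32 − 28 = 4 (magnesium high, magnesium low, GGT high, CPK high). The SAP adds none of its own.

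**2. Which missing limits concern collected tests?** Magnesium is not in protocol Table 5, so its two limits could never be applied: 32 − 2 = 30 usable limits, of which 28 are carried over. The remaining two are CPK and GGT. Both are in protocol Table 5 and both are named chemistry variables in SAP 10.3. Clinical labs are scheduled at Visit 1, Visit 3, Week 8 and Week 12/ET (protocol Table 4), so both tests have scheduled baseline and post-baseline values.

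**3. What CPK and GGT still receive**
- SAP 10.3.1: mean change to each visit and to the minimum, maximum and final value, compared between arms.
- SAP 10.3.2: subjects low or normal at baseline who are high at any post-baseline visit or at the final visit, for each variable with a reference range.

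The shift count treats a value just above ULN and a value above 5 x ULN (CPK) or 2.5 x ULN (GGT) alike. It also leaves out subjects already high at baseline who rise further. What is lost is therefore the count and listing at the protocol's own thresholds.

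**4. SAP Appendix B against the 12-week schedule.** Two of its rows, aPTT and INR, have no scheduled post-baseline draw. Protocol 5.3.1.1 says: "The PT/PTT will be performed only Screening Visit 1", and Table 5 marks PT/INR and PTT as Visit 1 only. Criteria with scheduled post-baseline data: 28 − 2 = 26.

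**5. SAP Appendix B against the Transition schedule**
- Scheduled tests: vitamin B12, vitamin B6, folic acid, MMA, homocysteine (5).
- Scheduled tests with a PCS criterion in either document: 0 of 5.
- SAP criteria with scheduled Transition data: 0 of 28.

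SAP 10.3.1 gives the special labs Transition mean changes. SAP 10.3.2 limits shift tables to the 12-week Treatment Period. No categorical laboratory display of these five tests remains for the Transition Period.

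**6. Cross-references.** SAP 10.3.3 (labs) cites Appendix C, which holds vital signs and weight. SAP 10.4.3 (vital signs and weight) cites Appendix B, which holds labs. The two pointers are interchanged.

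**The case against.** The strongest reply is that the protocol delegated the choice. Section 8.1.4.3 speaks of selected variables, and Appendix D is invoked in 5.3.1.1 for a different purpose, the site's duty to report or justify. That duty holds whatever the SAP tabulates. This stands, and it rules out calling the omission a protocol breach. It does not explain why these two tests alone were left out, or why nothing is said about it.

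Four stronger readings are tempting, and the documents do not support them.

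- *Marked CPK or GGT elevations would go unseen.* They would not. Both tests are in the mean-change and shift tables, and elevations reported as adverse events reach the tables in SAP 10.2.2. Only the PCS count and listing are lost.
- *The CPK omission weakens surveillance for neuroleptic malignant syndrome.* Protocol 3.2 lists that syndrome as an identified risk, but neither document links it to creatine kinase. Other anti-PD drugs except amantadine are tapered before Day 1, while scheduled post-baseline clinical labs come only at Week 8 and Week 12/ET.
- *Protocol Table 2 shows how many special-lab abnormalities would go unreported.* Its entries for vitamin B6 and homocysteine are adverse event frequencies over a mean of 854 days. Such events would still appear in the adverse event tables, including those that SAP 10.2.2 plans for the Transition Period.
- *The Transition summary will certainly be empty, and clotting tests are never repeated.* This holds for scheduled tests only. Protocol 5.5.1.2 permits discretionary laboratory tests, and protocol 5.1.2.2 requires Week 12 procedures at early termination, so stray values are possible.

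The aPTT and INR rows also keep a use, since the 10.3.3 listing covers any time in the study and so can include Visit 1 values. The swapped pointers are clerical: the appendix titles make the intended table plain.

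**Conclusion.** The point holds at minor severity, in two parts. First, of the 30 protocol PCS limits that apply to collected tests, 28 are in the SAP. The CPK and GGT limits are not, and no reason is given. Second, the Transition Period PCS laboratory summary has no scheduled input (0 of 28 criteria, 0 of 5 tests), and the special labs drawn in that period have no categorical laboratory display.

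The effect is confined to descriptive safety output. Efficacy inference, sample size and data collection are unaffected. The aPTT and INR rows and the appendix pointers are housekeeping and change no result.

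The conclusion assumes that the SAP Appendix B table as read here is complete, and that the Transition Period follows the schedule in protocol Table 4 and SAP 6.5.

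**What to change.** 1. In SAP Appendix B, add the protocol's own rows for CPK (> 5 x ULN) and GGT (> 2.5 x ULN). The table then has 28 + 2 = 30 criteria, every Appendix D limit that applies to a collected test.
2. In SAP 10.3.3, delete the Transition Period PCS laboratory summary. In SAP 10.3.2, extend the reference-range shift display to the Transition Period for vitamin B12, vitamin B6, folic acid, MMA and homocysteine, wherever the laboratory supplies a reference range. This needs no new threshold.
3. Housekeeping: footnote in Appendix B that aPTT and INR have no scheduled post-baseline value, and swap the appendix references in 10.3.3 and 10.4.3.

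The cost is a short SAP edit before database lock, two table rows and one shift table. The values are already collected under the current schedule, so no protocol change or extra sampling is needed.
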